Colonoscopy is the gold standard for detection of colonic polyps and colorectal cancer. Novel endoscopic enhancement by virtual electronic chromoendoscopy such as narrow-band imaging [NBI, Olympus, Japan], Fuji Intelligent Chromo Endoscopy [FICE, Fujifilm, Japan], i-scan [Pentax, Japan], techniques have been developed to aid endoscopists to better characterize colonic polyps and predict histology thus facilitating the adoption of the new paradigm of resect and discard i.e. the PIVI-ASGE strategy resulting in cost savings and avoidance of complications in patients. Several training modules have been developed and used in prior studies evaluating the performance of endoscopic image-enhancement technologies. Different training methods, have been evaluated and include face-to-face, interactive didactic teaching or web-based/computer-based self-learning teaching modules. The superiority of one training method over the other has not been well evaluated.

Trial Design

Multi-centre, international randomised controlled trial

Methodology

Participant Population

Participants will be consultants (gastroenterologists or surgeons) who are experienced in colonoscopy, training gastroenterologists, nurse endoscopists and junior doctors/medical students (who are naive in colonoscopy).

We aim to recruit 10-20 consultants/attending, 10-20 trainees/GI fellows, 10-20 nurse endoscopists (if applicable) and 10-20 junior doctors (non-GI trainees) from each centre. The participants will be randomised to receive self-directed computer based learning or face-to-face classroom didactic computer training module.

The above will be replicated at other centres: UK, USA, Italy, Germany and Japan.

Study duration: 2 years

Statistical Methodology

Performance characteristics of the participants for diagnosing colonic neoplastic vs. non neoplastic lesions (sensitivity, specificity, NPV, PPV and accuracy) will be calculated by comparing predicted histology with actual histology for all polyps and for those diagnosed with high confidence.. These performance characteristics between the two groups (face-to-face classroom training vs. self training module) will be compared using the Fisher's exact test. A P value of <0.05 will be considered to be statistically significant. *Kappa* statistic will be used to determine inter-observer agreement in polyp video classification during the training session.

Sample size

Assuming a non-inferiority trial with one-sided distribution (face to face training versus computer based training), and power of 90% the sample size is 375 observations (observation=1 video scored). This falls to 271 observations if 0.80 1-beta error is set. As we will use 60 videos per participants, we would need a minimum of 7 participants in each centre. To minimise any potential errors we aim to recruit 10-20 participants from each group (as described above) from each centre.

Objectives

To assess the impact of didactic face-to-face training vs. self-directed computer based training module.

To evaluate the impact of an educational training module has on the ability of clinicians to differentiate small/diminutive polyps.

Outcome Measures

A pre-training assessment will be completed by participants. Performance at predicting histology (neoplastic vs. non-neoplastic) will be assessed using sensitivity, specificity, PPV, NPV and accuracy. The proportion of high and low confidence diagnoses will be also documented.

Following training, participants will immediately complete a post-training assessment and performances will be observed comparing with pre-training assessment. A follow up assessment at 6 months will be completed to assess the retention and sustainability of skills acquired.

Kappa inter-observer variability between the raters will be assessed.

Intervention

Training module: didactic face-to-face classroom training or computer-based self-learning training module

Trial Schema

[figure not shown]

Table of Contents

Protocol development and sign off	2
Key Protocol Contributors	2
[name]	2
[name]	2
[name].....	2
Protocol Amendments	2
CI Signature Page.....	3
Sponsor statement:.....	3
Administrative Information	5
Trial Summar	7
Title	7
Diminutive polyp training module using novel endoscopic imagin: a comparison between didactic training and self-directed computer based training	7
Trial Design	7
Objectives	7
Participant Population and Sample Size	Error! Bookmark not defined.
Outcome Measures	8
Intervention	Error! Bookmark not defined.
Trial Schema	10
Table of Contents.....	11
1. Background and Rationale.....	13
1.1. Trial Rationale	16
1.2. Justification for participant population.....	16
1.3. Justification for design	17
2. Aims, Objectives and Outcome Measures.....	17
2.1. Aims and Objectives	17
2.2. Outcome Measures.....	17
3. Trial Design and Setting	17
3.1. Trial Design.....	17
3.2. Trial Setting	17
4. Eligibility	17

Colonoscopy is the gold standard for screening for bowel cancers and detection of precursors to colorectal cancer (polyps). Early detection of polyps, allows endoscopic removal and therefore reduction in colorectal cancer. With improvements in technology endoscopists are detecting more lesions within the bowel with the majority small/diminutive <5mm (80%), however the clinical relevance of these lesions is minimal as the risk of advanced histology or cancer is <1%^{1,2,3}. The current practice involves removing these lesions and sending for histopathological assessment, incurring a significant risk to the patient, cost and is time-consuming, with very little benefit^{4,5}. Novel imaging techniques including Narrow-band imaging (NBI-Olympus, Japan), i-Scan Optical enhancement (OE-Pentax, Japan) and Blue-light laser imaging (BLI- Fujifilm, Japan) can help endoscopists characterise these small lesions between being neoplastic and non-neoplastic (hyperplastic)^{6,7,8,9}. NBI involves the narrowing of bandwidths of light using a light filter. The light at this end of the spectrum is absorbed by haemoglobin (protein found within blood) therefore making blood vessels more pronounced. During the process whereby a polyp develops and later becomes neoplastic, there is an increase in blood vessels compared with normal tissue or hyperplastic polyps (benign), therefore NBI can be used to detect such lesions^{10,11}. I-Scan OE is an alternative imaging technique which enhances the pattern of the surface of polyps as well as the blood vessels, by manipulating dark-light borders and red, blue and green components of light. Blue laser imaging (BLI) is also new system for image-enhanced endoscopy using laser light. Blue laser imaging utilizes two monochromatic lasers (410 and 450 nm) instead of xenon light. A 410 nm laser visualizes vascular microarchitecture, similar to narrow band imaging, and a 450 nm laser provides white light by excitation.

These novel technologies have been demonstrated to be superior over standard white light endoscopy with NBI the most extensively investigated. A systematic analysis of 6 studies >500 polyps, resulted in a pooled sensitivity of 92%, spec 86%, accuracy of 89% at differentiating neoplastic from non-neoplastic lesions when using NBI¹². Head to head studies of NBI versus white light endoscopy (WLE) have shown NBI is better at differentiating between neoplastic and non-neoplastic lesions^{10, 13, 14}. Similar results have been found with i-Scan, with performances better than WLE and like NBI are similar to chromoendoscopy (a technique that involves spraying dye over bowel mucosa which is time-consuming and costly)^{15, 16}. BLI is a newer imaging platform, with the current evidence suggesting it is effective at differentiating polyps (neoplastic versus non-neoplastic) with

accuracies of 95.2%¹⁷, and when comparing with white light endoscopy the miss rate of adenoma was significantly lower with BLI (1.6% versus 10.0% p=0.001)¹⁸.

In order to characterise between neoplastic and non-neoplastic lesions, endoscopic scoring systems have been developed to assist endoscopists. Examples include NICE (NBI International Colorectal Endoscopic)³ (Appendix 1).

Recently Iacucci et al have developed a simplified classification system (SIMPLE- Simplified Identification Method for Polyp Labelling during the Endoscopy) for optical diagnosis of small and diminutive adenomas, SSA/Ps and hyperplastic polyps using the newly introduced OE-iSCAN system which achieved a high degree of diagnostic accuracy for small/diminutive polyp diagnosis. Furthermore, they have showed that a training module on SIMPLE classification resulted in an overall NPV of 91.3%¹⁹. This user-friendly classification system can be used by experienced and non-experienced gastroenterologists on multiple endoscopy imaging platforms to differentiate neoplastic from non-neoplastic polyps (Appendix 1). A classification system developed by Bisschops R et al recently using BLI called BASIC (BLI Adenoma Serrated International Classification). This takes into account the polyp surface, pit appearance and vessels, which has shown to have a high concordance amongst experts²⁰.

In the hands of experts using NBI-NICE classification system accuracies of 98.9%, sensitivity 98%, specificity 100%, NPV 97.7% and PPV100% were demonstrated when diagnosis was made with high confidence. Essential to the adopted use of these classifications is training for endoscopists, both experienced and those in training. There is good evidence that there is a short learning curve involved when using NBI²¹. One study using a self-administered computer based training module, community based gastroenterologists (non-expert) were able to reach excellent NPV of >90% but fell short of other requirements (prediction of surveillance intervals)²². Much like NBI, the learning curve at acquiring the skills in order to differentiate between hyperplastic and adenomatous lesions using i-Scan has been investigated. An early study by Neumann et al demonstrated a rapid learning curve with 4 endoscopists without previous experience with i-scan reached an accuracy of at least 85% after reviewing 67-110 lesions (with individualised feedback) following a 1 hour teaching session on pit pattern analysis²³.

There have attempts at identifying the most effective training tool and method at teaching non-experts how to characterise lesions effectively. Studies have used still images of lesions²⁴,

however this is limited as it does not reflect real-life practice as it does not allow views from different angles. It is thought videos simulate real-life practice as close as possible. A study using videos has demonstrated trainees were able to achieve accuracies of 90%²⁵.

More recently Rastogi's group sought to identify which training method was more effective in prediction of diminutive polyp histology amongst trainees: didactic face to face training versus computer-based self-learning ²⁶. The participants were randomised to either receive didactic training in the form of a classroom training session or self-learning via computer-based material on characterisation of polyps using NBI. Trainees reviewed 40 videos of diminutive polyps with the histology being revealed and explained. Both groups were given a further 40 videos for testing. This study found those taught in the didactic group characterised polyps with higher confidence, but the overall performance was similar in the two groups. The accuracy and sensitivity were slightly better in the self-learning group (93.9% vs 85.7% p 0.01 and 95.0% vs 86.9%; p0.03 respectively) in those polyps assessed with high confidence. This study demonstrates that a computer-based training module can be as effective in didactic training, perhaps a reflection on the amount of online self-learning trainees are exposed to.

We aim to recruit participants to receive either didactic face-to-face training or self-directed computer based learning, whereby participants will be taught how to characterise lesions using the NICE, BASIC and SIMPLE classification. We aim to recruit trainees, novice endoscopists and experienced endoscopists to compare the different groups. Pre- and post-training assessments will be completed allowing us to examine the impact of training, which will consist of 40-60 videos (equal proportion of NBI, iScan OE and BLI) in the pre-training assessment and 40-60 videos (different set of videos but also equal proportion of NBI, iScan OE and BLI) in the post-training assessment. A follow up assessment will be completed at 6 months to assess the retention of skills and sustainability of colonic polyp characterisation using the optical diagnosis techniques. An existing library of NBI and OE-iScan videos will be used and further videos will be collected during routine colonoscopies with patients consenting for images to be used for teaching purposes.

1.1. Trial Rationale

We hypothesise that following the training module there will be an improvement in performance between the pre-training and post-training assessments. We also hypothesise that there will be no difference between the didactic face-to-face group and the self-training group.

This is an important study as better characterisation of small polyps may eventually lead to a 'resect and discard' strategy in the future. This involves characterising small or diminutive polyps (<10mm) as either non-neoplastic or neoplastic, resecting the lesion but not sending for histopathological analysis, which has significant cost savings. In order to do this training is essential. Whilst didactic training is attractive, it is costly and resource heavy. The option of self-directed learning is an attractive one as it can be delivered at times that suit the user, at their pace and can be delivered in greater volumes.

This study is unique as it is examining the impact of the training module on different groups of participants (novice, training and experienced endoscopists), using multiple endoscopic platforms (NBI, i-Scan OE and BLI) at a multicentre, international level. It will enable us to assess whether the training module improves performance using different imaging modalities.

1.2. Justification for participant population

The participants included will be those that will need better polyp characterisation in everyday endoscopic practice, so they are ideal candidates. Novice endoscopists will be invited to examine the effect of the training module on participants without previous experience.

1.3. Justification for design

The training module will be carried out on the same day as the post-training assessment, in order to avoid any bias with erosion of knowledge/skills over time.

2. Aims, Objectives and Outcome Measures

2.1. Aims and Objectives

Hypothesis: performances at predicting the histology of small/diminutive polyps improves following both the didactic face-to-face feedback training and self-directed computer based training. We also hypothesise that there will no overall difference between the two teaching groups.

2.2. Outcome Measures

Outcome measures will include accuracy of polyp prediction, sensitivity, specificity, positive predictive value and negative predictive value. Proportion of high confidence diagnoses will also be recorded. Kappa statistics will be used to determine interobserver agreement in polyp video classification.

3. Trial Design and Setting

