6.2. Schedule of Assessments

Participants who agree to take part in the study will complete a pre-training assessment prior to the training day. Assessment material will be uploaded on REDCap, hosted via the University of Birmingham. Each participant will receive a link via email to complete the assessments. Each participant will be asked to assess: Quality of video High/Low, NICE classification, SIMPLE classification, BASIC classification, High/Low confidence and Hazewinkel criteria for each video. This will be completed at least 2 weeks prior to the training day. On the training day participants will receive either didactic face-to-face feedback training or computer-based training (identical). A post-training assessment will be completed within 72 hours of training (same videos as pre-training but in a different randomised order). The website will self-populate the data in Microsoft Excel documents. Participants will then be invited to complete a final assessment at 3-4 months, which will conclude the study.

7. Data Handling and Record Keeping

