9.1. Statistical Analysis

Performance characteristics of the participants for diagnosing colonic neoplastic vs. non neoplastic lesions (sensitivity, specificity, NPV, PPV and accuracy) will be calculated by comparing predicted histology with actual histology for all polyps and for those diagnosed with high confidence.. These performance characteristics between the two groups (face to face classroom training vs. self-training module)will be compared using the Fisher's exact test. A P value of <0.05 will be considered to be statistically significant. *Kappa* statistic will

be used to determine inter-observer agreement in polyp video classification during the training session.

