9.1.3. Planned Final Analyses

Final analysis will take place after the initial training day and after the 6-month follow up assessment.

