9.1.4. Power Calculations

Assuming a non-inferiority trial with one-sided distribution (face-to-face training versus computer based training), and power of 90% the sample size is 375 observations (observation=1 video scored). This falls to 271 observations if 0.80 1-beta error is set. As we will use 60 videos per participants, we would need a minimum of 7 participants in each centre. To minimise any potential errors we aim to recruit 14 participants from each centre (7 randomised to face-to-face training and 7 to the computer group).

10. Trial Organisational Structure

There is no trial steering committee needed for this teaching project, The members involved are outlined in the administrative information at the start of this protocol.

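### No primary outcome is named: at least ten arm comparisons share one P<0.05 rule, and the stated power is tied to none of them

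*Combined protocol and SAP*

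**What the plan says.** - **Measures.** Section 2.2: "Outcome measures will include accuracy of polyp prediction, sensitivity, specificity, positive predictive value and negative predictive value". The proportion of high-confidence diagnoses and kappa follow. The Trial Summary lists the same five. List order is no guide to priority: accuracy comes first in 2.2 but last in the Trial Summary and in 9.1.
- **Polyp sets, test and threshold.** Section 9.1 obtains the measures by "comparing predicted histology with actual histology for all polyps and for those diagnosed with high confidence". The arms "will be compared using the Fisher's exact test", and "A P value of <0.05 will be considered to be statistically significant". It names no time point, testing order or adjustment.
- **Analysis times.** Section 9.1.3: "Final analysis will take place after the initial training day and after the 6-month follow up assessment".
- **Source of the prediction.** Under section 6.2 each participant records "NICE classification, SIMPLE classification, BASIC classification, High/Low confidence and Hazewinkel criteria for each video". Section 9.1 does not say which classification feeds the arm comparison. Section 9.1.2 plans to compare the three classifications with each other.
- **Power.** Section 9.1.4 begins "Assuming a non-inferiority trial with one-sided distribution" and gives 375 observations for 90% power and 271 for 80%. It states no measure, expected rate, margin or alpha.
- **Hypotheses.** Sections 1.1 and 2.1 expect improvement after training in both arms and no difference between them.

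**The concern.** With one threshold and many unranked comparisons, the plan does not say which result decides the trial. Two things are at stake.

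First, the chance that at least one comparison crosses P<0.05 when the arms are truly equal is larger than the threshold suggests.

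Second, the hypothesis of no overall difference cannot be settled when measures disagree. The Background describes an earlier randomised trial of the same two training methods in which this happened. Overall performance was similar, yet in high-confidence polyps accuracy was 93.9% vs 85.7% (p 0.01) and sensitivity 95.0% vs 86.9% (p 0.03), both favouring self-learning. If this trial repeated that pattern, the plan could not say whether its hypothesis had been supported or refuted.

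The choice of classification adds to the openness. Section 7.1 and Appendix 1 show that SIMPLE has a category for sessile serrated lesions, while NICE has hyperplastic, adenoma and invasive cancer. The same video can therefore yield different calls.

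**Working it through.** **1. Can the sample size reveal the intended outcome?** For non-inferiority of two equal proportions p with margin δ, n per arm = 2p(1−p)(z₁₋α + z₁₋β)²/δ².

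- The 90%/80% ratio depends only on alpha. One-sided 0.05 gives (1.645+1.282)²/(1.645+0.842)² = 8.564/6.183 = 1.385. The plan's ratio is 375/271 = 1.384. One-sided 0.025 gives 1.339, which would turn 375 into 280 rather than 271. One-sided 0.05 is therefore the likely alpha.
- Rate and margin cannot be recovered. Pairs that come close include p = 68%, δ = 10 points (373/270 per arm), p = 83%, δ = 8 points (378/273 per arm), and p = 57%, δ = 15 points (374/270 in total).
- The measures also rest on different numbers of videos. If 60% were neoplastic (assumed), 375 observations would give 375 × 0.6 = 225 for sensitivity and 150 for specificity. One figure cannot power all five equally.

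**2. Count of arm tests.** 5 measures × 2 polyp sets = 10 (section 9.1). If repeated at both analyses of section 9.1.3, 10 × 2 = 20. This leaves out the high-confidence proportion, kappa and the classification comparisons.

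The follow-up date conflicts: section 6.2 says "Participants will then be invited to complete a final assessment at 3-4 months", while the Trial Summary, Background and sections 8 and 9.1.3 say 6 months. These must be reconciled, but there is one follow-up either way, so the count is unchanged.

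**3. Reference for independent tests.** 1 − 0.95ᵏ = 40.1% for k = 10 and 64.2% for k = 20. The measures and sets overlap heavily, so these are not estimates for this trial.

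**4. Simulation with no true arm difference, allowing for the overlap.** From the documents: 60 videos per participant and 7 per arm per centre. Assumed: 35 per arm (five centres × 7), the rates shown, and independent readings. The test is a two-sided continuity-corrected chi-square, a close proxy for Fisher's test, with 3000 runs per row.

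| Per arm | Neoplastic | Sens/spec | High confidence | Correlation over time | Accuracy alone | Any of 10 | Any of 20 |
|---|---|---|---|---|---|---|---|
| 7 | 60% | 90/80% | 70% | 0 | 3.7% | 12.5% | 23.3% |
| 7 | 60% | 90/80% | 70% | 0.8 | 3.8% | 13.0% | 21.8% |
| 35 | 60% | 90/80% | 70% | 0 | 4.2% | 14.8% | 27.0% |
| 35 | 60% | 90/80% | 70% | 0.8 | 4.3% | 15.7% | 27.1% |
| 35 | 60% | 90/80% | 50% | 0.5 | 4.4% | 17.1% | 30.4% |
| 35 | 60% | 90/80% | 90% | 0.5 | 4.3% | 12.2% | 22.8% |
| 35 | 50% | 85/85% | 70% | 0.5 | 4.2% | 15.2% | 27.6% |

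A separate simulation with Fisher's exact test itself gave 11–16% for ten tests, 20–29% for twenty and 2–5% for accuracy alone. Taken together: about 11–17% and 20–30%.

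**The case against.** **The plan never claims a trial-wide 5%.** A reader might infer that it promises a 5% overall error rate and breaks it. It does not: section 9.1 sets a per-test threshold only. This objection stands. The figures show what the unranked rule produces, not a breached commitment.

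**Twenty tests is a reading, not a specification.** Section 9.1 names no time point, and the Trial Summary describes the follow-up as a check on retention of skills, which may be a within-participant question. This also stands. Ten tests are firm; twenty is conditional.

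**A false difference is not the error that most threatens this hypothesis.** A spurious P<0.05 would usually count against the expected result of no difference. The error that would falsely support it is a non-inferiority or no-difference claim on a measure picked afterwards. That risk is related but was not computed, and the percentages above must not be read as measuring it. Nor was any extra inflation from choosing among the three classifications computed.

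**The documents do not point to a particular primary outcome.** A reader might take accuracy, or SIMPLE, as the evident choice. The Background also gives weight to negative predictive value, and all three classifications are taught. The choice belongs to the authors.

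None of this supplies a primary outcome, a testing order or a measure behind the power statement.

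**Conclusion.** The point holds. No outcome is primary, ten arm comparisons share one threshold (twenty if both analysis times are tested), the 90% power is tied to none of them, and the source of the predicted histology is left open.

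The chance of at least one false arm difference is about 11–17% for ten tests, or roughly 2 to 3.5 times 5%. For twenty it is about 20–30%, or 4 to 6 times. One named test stays at or below 5%. The documents give none of the underlying rates, so these are ranges under assumptions: sensitivity and specificity about 80–90%, 50–70% neoplastic, 50–90% high confidence, and independent readings. The 64% for twenty independent tests is tempting to quote, but it ignores the overlap between the measures and should not be used.

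The 5% for a single test also depends on independent readings. With an assumed latent reader correlation of 0.02–0.10, ignored by Fisher's test, accuracy alone was falsely significant in 8.5–27.4% of runs and at least one of twenty tests in 36–55%. Clustering is a separate defect, which naming a primary outcome will not cure.

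**What to change.** In sections 2.2 and 9.1, name one primary measure, in one polyp set, at one time point, from one named classification. One possibility is accuracy over all videos at the first post-training assessment, with the authors choosing the measure and the classification. In section 9.1.4, restate the calculation for that outcome, with its expected rate, margin and alpha.

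Report the other measures, the high-confidence set and the follow-up as secondary with 95% confidence intervals, or under a pre-stated testing order. If all comparisons were to stay confirmatory, a Bonferroni threshold would be 0.05/10 = 0.005 for ten or 0.05/20 = 0.0025 for twenty. State whether arms are compared at follow-up, and reconcile its date.

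Naming the primary outcome changes only wording and adds no data collection. The restated calculation may or may not return 375. The downside is that secondary measures can no longer support a stand-alone claim.
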